Early reports from many centers across the country and other countries appear to indicate that the Synergy IOL implanted bilaterally is yielding very good results at all ranges, particularly at near.²⁻⁴ Anecdotally, some surgeons have reported excellent near vision with good but not great distance vision.

Prior to utilizing the Synergy IOL, our center along with many high-volume centers across the country, employed a mix and match strategy utilizing the TECNIS Symphony in the dominant eye and the TECNIS Multifocal in the non-dominant eye with good results and high patient satisfaction.⁵

We propose conducting a prospective evaluation of a mix and match strategy incorporating Symphony with InteliLight in the dominant eye and Synergy IOL in the non-dominant eye. The Symphony lens, an Extended Depth of Focus (EDOF) lens, known for its superior distance and intermediate vision, has been upgraded to the OptiBlue version (InteliLight). The Symphony with InteliLight has an enhanced echelette design and a violet light filter. The upgraded echelette design utilizes a high-resolution lathing process that helps reduce light scatter and halo intensity. The violet light filter is designed to mitigate halo, glare, and starbursts.

1. OBJECTIVE:

The purpose of this study is to evaluate the visual outcomes, visual disturbances, patient satisfaction and spectacle independence of the Symphony with InteliLight when implanted in

the dominant eye and a Synergy is implanted in the non-dominant eye in patients with or without astigmatism after routine cataract surgery.

2. STUDY ENDPOINTS:

1. Primary Endpoints:

Binocular defocus curve at 3 months

2. Secondary Endpoints:

- a. Monocular and binocular uncorrected and distance-corrected near at 40 cm visual acuity at 3 months.
- b. Monocular and binocular uncorrected and distance-corrected near at 33 cm visual acuity at 3 months
- c. Monocular and binocular uncorrected and distance-corrected intermediate (66 cm) visual acuity at 3 months
- d. Monocular and binocular uncorrected and best-corrected distance (4 m) visual acuity at 3 months
- e. To evaluate patient's vision satisfaction at 3 months
- f. To evaluate patient's spectacle independence at 3 months
- g. To evaluate visual symptoms using a questionnaire at 3 months
- h. To evaluate functional vision using a questionnaire at 3 months

3. STUDY DESIGN:

Prospective, multicenter (up to 2 site in US), non-randomized, bilateral eye study.

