4. INCLUSION/EXCLUSION CRITERIA

4.1. Inclusion Criteria:

Subjects **MUST** fulfill the following conditions to qualify for enrollment into the trial

1. Subject is undergoing bilateral lens extraction with intraocular lens implantation of the Symphony with InteliLight in the dominant eye and a Synergy in the non-dominant eye.
2. Gender: Males and Females.
3. Age: 50 years and older.
4. Willing and able to provide written informed consent for participation in the study
5. Willing and able to comply with scheduled visits and other study procedures.
6. Scheduled to undergo standard cataract surgery with topical anesthesia in both eyes within 2 to 30 days between surgeries
7. Subjects who require an IOL power in the range of +5.00 D to +34.0 D only.
8. Subjects who require a toric IOL up to +3.75 D at the IOL plane (2.57 D corneal plane).
9. Potential postoperative visual acuity of 0.2 logMAR (20/32 Snellen) or better in both eyes.

4.2. Exclusion Criteria:

Subjects with **ANY** of the following conditions on the eligibility exam may **NOT** be enrolled into the trial.

1. Severe preoperative ocular pathology: amblyopia, rubella cataract, proliferative diabetic retinopathy, shallow anterior chamber, macular edema, retinal detachment, aniridia or iris atrophy, uveitis, history of iritis, iris neovascularization, medically uncontrolled glaucoma, microphthalmos or macrophthalmos, optic nerve atrophy, macular degeneration (with anticipated best postoperative visual acuity less than 20/30), advanced glaucomatous damage, etc.
2. Uncontrolled diabetes.
3. Use of any systemic or topical drug known to interfere with visual performance.
4. Contact lens use during the active treatment portion of the trial.
5. Any concurrent infectious/non-infectious conjunctivitis, keratitis or uveitis.
6. Clinically significant corneal dystrophy
7. History of chronic intraocular inflammation.
8. History of retinal detachment.
9. Pseudoexfoliation syndrome or any other condition that has the potential to weaken the zonules.
10. Previous intraocular surgery.
11. Previous corneal refractive surgery (i.e. LASIK, PRK, RK).
12. Previous keratoplasty
13. Severe dry eye
14. Pupil abnormalities
15. Anesthesia other than topical or peribulbar anesthesia (i.e. retrobulbar, general, etc).
16. Any clinically significant, serious or severe medical or psychiatric condition that may increase the risk associated with study participation or may interfere with the interpretation of study results.

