17. Participation in (or current participation) any ophthalmic investigational drug or ophthalmic device trial within the previous 30 days prior to the start date of this trial.

The principal investigator reserves the right to declare a patient ineligible or non-evaluable based on medical evidence that indicates the patient is unsuitable for the trial.

4.3. Exclusion Criteria at time of surgery:

If any of the following exclusion criteria are applicable to the study eye, the subject should not continue in the study.

1. Other ocular surgery procedures, i.e. iStent, anterior vitrectomy
2. Significant vitreous loss
3. Significant anterior chamber hyphema
4. Uncontrollable intraocular pressure
5. Zonular or capsular rupture

6. Bag-sulcus, sulcus-sulcus or unknown placement of the haptics
7. Suturing of incision required at time of surgery
8. Intraocular lens tilt or decentration
9. Significant sedation or retrobulbar block during surgery
10. Other procedure, such as pupil stretch, expanders, iris hooks during surgery

Note: Any subject in which surgery has been aborted for either eye should immediately be discontinued from the study and an exit form completed for that subject. These subjects will be followed up as per the clinic standard of care, monitored for safety, and their data will be excluded from the study efficacy analysis (obtained from FDA Database Research Results Feb, 05, 2009). All adverse events will be appropriately documented and reported.

Additionally, participants who are considered to be a vulnerable subject population are not to be enrolled into the study without prior written authorization from both the Sponsor and the IRB to ensure that a description of additional safeguards are in place during the consenting and enrollment processes. Vulnerable populations include, but are not limited to, the following:

1. Prisoners
2. Nursing home residents /institutionalized individuals
3. Mentally disabled /cognitively impaired individuals
4. Sponsor employees and their family members
5. Site employees and their family members that are directly and indirectly involved with the study
6. Students of the university or the principal investigator participating in the study
7. Economically and/or educationally disadvantaged individuals
8. Comatose individuals / traumatized individuals
9. Adults who do not read and/or write
10. Hearing impaired individuals
11. Terminally ill individuals / individuals with life-threatening conditions

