1. Visit 1: Screening and enrollment: Preoperative evaluation completed not more than eight weeks before surgery
2. Visit 2: Day of Surgery for each eye
3. Visit 3: Month 3: 90 ±15 days postoperative after second eye surgery

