6.2. Statistical Analysis

All data will be collected by the site and entered into a database. Subjects will be assigned an ID number. Data analysis will be performed without patient identification. Statistical analysis will be performed using standard descriptive statistics and other tests as deemed appropriate based on the characteristics of the data to be analyzed. All statistical tests will be two-sided and interpreted at a 5% significance level. Vision satisfaction, spectacle independence and visual symptoms will be compared to a historical control of patients implanted bilaterally with Synergy OU. Data analysis will be conducted by a third-party consultant.

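### Section 6.2 tests three secondary patient-reported outcomes against a historical bilateral Synergy group that the plan neither defines nor aligns with the study cohort, so p<0.05 could not be attributed to the lens combination

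*Combined protocol and SAP*

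**What the plan says.** The historical control appears once in the document, in section 6.2: "Vision satisfaction, spectacle independence and visual symptoms will be compared to a historical control of patients implanted bilaterally with Synergy OU". Its source, size, sites, period, eligibility, questionnaires, assessment time and data level (patient records or published summaries) are not given.

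The same section sets the level for all testing: "All statistical tests will be two-sided and interpreted at a 5% significance level". The method is descriptive statistics plus "other tests as deemed appropriate based on the characteristics of the data to be analyzed", which neither plans an adjustment nor rules one out.

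The three outcomes are secondary endpoints e, f and g in section 2; endpoint g, for example, reads "To evaluate visual symptoms using a questionnaire at 3 months". The primary endpoint, the binocular defocus curve, is not part of this comparison. The objective in section 1 states no comparative hypothesis. Section 3 describes a non-randomized study, and section 6.1 calls it a pilot of 40 subjects.

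**The concern.** The study cohort is selected and assessed under specific rules. Section 4.1 item 9 requires "Potential postoperative visual acuity of 0.2 logMAR (20/32 Snellen) or better in both eyes", and 4.2 lists 17 exclusions. Section 4.3 then filters again on the day of surgery: "If any of the following exclusion criteria are applicable to the study eye, the subject should not continue in the study". One of its ten items is "Intraocular lens tilt or decentration". Questionnaires are completed at Visit 3, which 5.4.1 places at "90 ±15 days postoperative after second eye surgery".

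The plan asks none of this of the historical patients. A series that kept eyes with complications, used another satisfaction or symptom instrument, or asked its questions at another time could differ from the study cohort with no difference between lens strategies.

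This is the only efficacy comparison with another lens strategy that 6.2 names, and section 12 says the results will be submitted for publication. A reader given p<0.05 could take a difference in cohort, instrument or timing for a lens effect.

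**Working it through.** **1. What the plan fixes for each group**

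| Feature | Study cohort | Historical bilateral Synergy group |
|---|---|---|
| Clinical eligibility | 4.1, 4.2 | not stated |
| Surgery-day filter | 4.3 | not stated |
| Questionnaires | by domain only, no instrument named (5.4.2) | not stated |
| Timing | 90 - 15 = 75 to 90 + 15 = 105 days after the second eye (5.4.1) | not stated |
| Number | 40 (6.1) | not stated |
| Adjustment or matching | not stated | not stated |

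**2. The plan's own figure.** The 40 subjects come from a rule of thumb of at least 30 (6.1), which 40 meets. Section 6.1 says the outcome SD is unknown. No effect size, power or control number is given, so no figure exists to reproduce for this comparison.

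**3. How a cohort shift becomes a significant result.** From the document: 40 study patients and a two-sided 5% level. Assumed: 40 or 100 controls, no lens effect, and a shift between cohorts from other causes.

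*Outcome scored on a scale, shift d in SD units.* SE = sqrt(1/40 + 1/n_c), which is 0.2236 for 40 controls and 0.1871 for 100. Normal approximation: P(p<0.05) = Φ(d/SE - 1.96) + Φ(-d/SE - 1.96). For d = 0.2:

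- 40 controls: d/SE = 0.894, so Φ(-1.066) + Φ(-2.854) = 14.5%.
- 100 controls: d/SE = 1.069, so Φ(-0.891) + Φ(-3.029) = 18.8%.

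The two-sample t test (noncentral t) gives nearly the same:

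| Shift | 40 controls | 100 controls |
|---|---|---|
| 0 | 5.0% | 5.0% |
| 0.1 SD | 7.3% | 8.3% |
| 0.2 SD | 14.3% | 18.6% |
| 0.3 SD | 26.3% | 35.7% |

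*Yes/no outcome, one group at an assumed 80%.* Exact enumeration over both binomial distributions. Ranges cover shifts up and down, with either group at 80%. Fisher's test is shown because it is the only test the protocol names (6.3, for adverse events); it is not planned for these outcomes.

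| Shift | 40 controls: Fisher / pooled z | 100 controls: Fisher / pooled z |
|---|---|---|
| none | 2.8% / 5.1% | 3.7% / 5.0% |
| 5 points | 5.2-5.5% / 8.4-9.2% | 7.3-9.7% / 8.4-12.1% |
| 10 points | 12-16% / 18-25% | 19-32% / 21-36% |

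With a shift present, more controls raise the rejection rate: they reduce sampling error and leave the bias as it was. With a small shift, 40 controls and Fisher's test, the rate stays near 5%.

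**4. Precision of the comparison.** With 80% in both groups, the 95% CI half-width is 1.96 × sqrt(0.16/40 + 0.16/n_c): 1.96 × 0.0894 = 17.5 points for 40 controls, and 1.96 × 0.0748 = 14.7 points for 100. These intervals cover sampling error only.

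**The case against.** Four points can fairly be made in the plan's defence.

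- **Silence is not misalignment.** A reader might infer that the historical group does differ from the study cohort. The documents never describe it, so they cannot show that. It could prove closely comparable. This stands, and limits the point to what the plan fails to define and require.
- **No decision rule.** A reader might infer that 6.2 sets up a superiority decision on these outcomes. It does not: no success criterion or claim is attached to them, no test is named for this comparison, and a purely descriptive comparison is a possible reading. The blanket 5% sentence makes testing the more natural one.
- **The study is modest about itself.** It is a non-randomized pilot with a non-comparative objective, and these outcomes are secondary. That lowers the stakes. But the pilot label is used in 6.1 to explain the sample size; it neither marks these comparisons as exploratory nor limits how 6.2 may be read.
- **The rejection rates are hypothetical.** Only the 40 and the 5% come from the document. Control size, the 80% rate, the shifts and the outcome scale are assumed. This also stands: the figures show how the problem scales and do not estimate this trial's error.

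Historical records may also lack surgery-day details or a 75-105 day visit, so the remedy has to allow for incomplete data.

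**Conclusion.** The concern holds in a limited form. As written, 6.2 allows a 5% comparison with an undefined, non-concurrent group, with no alignment of eligibility, questionnaire or timing and no stated adjustment. A p-value below 0.05 could not then separate the lens combination from differences in cohort, instrument or timing. That conclusion follows from the design and needs no assumed number.

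The size cannot be determined from the documents. Under the assumptions above, the nominal 5% test rejects from about 5% of the time (5-point shift, 40 controls, Fisher) to about 36% (10-point shift with 100 controls and pooled z, or 0.3 SD with 100 controls).

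The issue is confined to three secondary outcomes. It does not touch the primary endpoint, and nothing in the documents supports saying that the comparison will be biased or in which direction. The change should be made because it is cheap; the study does not depend on it.

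**What to change.** Amend section 6.2 as follows.

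1. Name the source and number of historical controls, and say whether patient-level data are available.
2. Where the information was recorded, restrict controls to patients who meet the clinical and surgery-day criteria of 4.1-4.3. The consent, visit-willingness, trial-date and lens-assignment items do not apply. Require the same questionnaires, completed about 75-105 days after second-eye surgery.
3. Use a two-sample analysis, so that the controls' own sampling error is counted. Where patient-level data exist, adjust for prespecified baseline variables available in both groups, for example age, toric status and the Visit 1 score on the same questionnaire.
4. Report each difference with a 95% CI, label it exploratory, and make no superiority or similarity claim from the p-value alone. State that residual case-mix bias cannot be excluded, especially if only summary control data exist.

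The cost is SAP wording and modest analysis work, with no new patients or visits. Some controls may be lost and the intervals will widen; adjustment may be impossible with summary-only data; and the conclusion on these three outcomes becomes exploratory.

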5.4.2. Measurements and evaluations

1. Visit 1: Informed consent process will be conducted at this visit. Assessments include best-corrected Snellen visual acuity, intraocular pressure (IOP), slit lamp examination including dilated fundus exam, cataract density and type, and visual symptoms, patient satisfaction, spectacle independence and visual function

questionnaires. Any testing that is part of the site’s preoperative cataract surgery standard of care evaluation may be performed prior to signing the informed consent provided these tests are conducted within 90 days of the surgery and notation of the date performed is entered onto the CRF. The surgeon’s standard pre-cataract surgery treatment will be used in all patients

2. Visit 2: The surgeon may use his preferred cataract extraction technique (manual or laser). The lens will be implanted in the bag. The following information will be captured the day of surgery: phaco technique (manual or laser), lens implanted and power, target refraction, residual astigmatism and axis for Toric Calculator (if applicable), additional surgical procedures, intraoperative complications, and any device deficiencies. The surgeon’s standard post cataract surgery treatment will be used in all patients.

Visit 3: Slit lamp examination, manifest refraction, monocular and binocular uncorrected as well as distance corrected visual acuities will be evaluated at 4 m, 66 cm, 40 cm, 33 cm and best distance, and defocus curve. Additionally, dilated fundus exam (as deemed necessary by the investigator), visual symptoms, patient satisfaction, spectacle independence and visual function questionnaires, adverse events and any device deficiencies will be evaluated.

Table 1. Study Visit Schedule and Assessments

| | Visit 1 Screening | Visit 2 and 2A DOS | Visit 3 3-Month 90 ±15 days |
|--------------------------------|----------------------|-----------------------|-----------------------------------|
| Informed Consent | X | | |
| Inclusion/Exclusion | X | X | |
| Demographics/Ocular history | X | | |
| BCVA Snellen | X | | |
| Eye dominance | X | | |
| UCVA ETDRS (4m) | | | X* |
| UCIVA ETDRS (66 cm) | | | X* |
| UCNVA ETDRS (40 cm) | | | X* |
| UCNVA ETDRS (33 cm) | | | X* |
| UCNVA ETDRS (at best distance) | | | X* |
| Manifest refraction – Max Plus | | | X |
| BCVA ETDRS (4m) | | | X* |
| DCIVA ETDRS (66 cm) | | | X* |

| | | | |
|--------------------------------|---|---|-----|
| DCNVA ETDRS (40 cm) | | | X* |

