6. STATISTICAL CONSIDERATIONS

6.1. Sample size

A total of 40 subjects will be enrolled. In order to calculate the sample size, we need to know an accurate estimate of the standard deviation of the outcome measure which we do not know; therefore, we consider this study a pilot trial. When estimating the sample size for a pilot study, the simplest method is to apply a sample size rule of thumb.

Browne suggests a general flat rule to 'use at least 30 subjects or greater to estimate a parameter'.

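### Should the primary defocus curve and the acuities also be compared with the historical bilateral-Synergy control?

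*Combined protocol and SAP*

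**What the plan says.** Section 2 lists one primary endpoint, "Binocular defocus curve at 3 months", and eight secondary endpoints, a to h. Items a to d are near (40 cm and 33 cm), intermediate and distance acuities. Items e to g are satisfaction, spectacle independence and visual symptoms. Item h is "To evaluate functional vision using a questionnaire at 3 months".

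Section 6.2 names a comparator for three of these: "Vision satisfaction, spectacle independence and visual symptoms will be compared to a historical control of patients implanted bilaterally with Synergy OU". Everything else falls under standard descriptive statistics and "other tests as deemed appropriate based on the characteristics of the data to be analyzed". Tests are two-sided at the 5% level. Section 6.3 plans a group comparison of adverse events only.

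The objective in section 1 begins: "The purpose of this study is to evaluate the visual outcomes, visual disturbances, patient satisfaction and spectacle independence". It goes on to name the mixed implantation and the patient population, and no comparator. On sample size, section 6.1 says the standard deviation is not known, and for that reason "we consider this study a pilot trial". The 40 subjects come from a flat rule of at least 30 for estimating a parameter.

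**The concern.** The background before section 1 reports very good early results with bilateral Synergy, particularly at near, and then adds: "Anecdotally, some surgeons have reported excellent near vision with good but not great distance vision". It goes on to propose a lens known for distance and intermediate vision in the dominant eye. A reader naturally asks whether the mixed pair sees better at distance than bilateral Synergy, and whether near vision differs.

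The sponsor has already chosen bilateral Synergy as the historical control but uses it only for questionnaire outcomes. The trial-side data would cost nothing extra, since at Visit 3 "monocular and binocular uncorrected as well as distance corrected visual acuities will be evaluated at 4 m, 66 cm, 40 cm, 33 cm", and the binocular defocus curve is measured at the same visit.

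Two things would be at stake. The trial would end without a planned estimate on a question its background raises. And the open clause on further tests could let someone pick a defocus level or test distance after seeing the results.

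**Working it through.** **1. Which endpoints are compared.** Section 2 gives 1 primary + 8 secondary = 9. Section 6.2 compares e, f and g, which is 3. The remaining 9 − 3 = 6 are the primary, a, b, c, d and h. No other section plans a vision comparison with bilateral Synergy, so the observation is factually correct.

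**2. Whether the plan owes such a comparison.**

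| Place | What it commits to |
|---|---|
| Background | Mentions the distance impression, marked as anecdotal |
| Section 1 | Evaluation of the lens pair, no comparator |
| Section 2 | Defocus curve and acuities at 3 months, no comparator |
| Section 6.1 | Pilot, sized to estimate a parameter |
| Section 6.2 | Descriptive statistics, plus three named historical comparisons |

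The distance remark is not carried into the objective or the endpoints. The other themes of the background, visual disturbances and patient satisfaction, are carried through and do have planned comparisons. Nor do the documents predict a binocular near loss. The statement in section 9.1 about possibly needing glasses at near describes the dominant-eye lens, and the same section describes the other eye's lens as giving a full range of vision.

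**3. The plan's own figure.** The 40 subjects satisfy the rule of at least 30. There is no power formula to reproduce.

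**4. What the descriptive analysis delivers.** The 95% half-width of a single-group mean is t(0.975, n − 1)/√n × SD. For n = 40 this is 0.320 SD. At assumed logMAR SDs of 0.08, 0.10 and 0.15 it is 0.026, 0.032 and 0.048.

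**5. What an added contrast would deliver.** The half-width is t(0.975, n + m − 2) × √(1/n + 1/m) × SD, with n = 40 and an assumed control size m:

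| m | Half-width (SD) | Detectable at 80% power (SD) |
|---|---|---|
| 30 | 0.482 | 0.68 |
| 40 | 0.445 | 0.63 |
| 100 | 0.370 | 0.52 |

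The last column is (z0.975 + z0.80) × √(1/n + 1/m). With m = 40, the half-width is 0.036, 0.045 and 0.067 logMAR at the three assumed SDs. Power for an assumed difference of 0.05 logMAR is 79%, 60% and 31%. These figures cover sampling error only; confounding and differences in measurement against a historical group come on top.

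**6. Multiplicity.** Count each compared outcome as one test at 5% and assume independence, for illustration only, since the outcomes come from the same patients. The three planned comparisons then carry a chance of at least one false positive of 1 − 0.95³ = 14.3%. Two added vision contrasts would raise it to 1 − 0.95⁵ = 22.6%. Adding contrasts increases the exposure to chance findings.

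**The case for a change.** The strongest case for the concern is that the comparator is already chosen, the trial-side measurements are already scheduled, and a few sentences could fix two exploratory contrasts in advance. That would limit later choice: under independence, at least one of two 95% intervals excludes zero by chance with probability 1 − 0.95² = 9.8%, against 1 − 0.95¹⁰ = 40.1% for ten.

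Part of this stands. The clause on further tests is open, and any vision contrast made under it would be unplanned and should be reported as such. But the documents plan no set of ten contrasts, so the 40.1% describes an assumed misuse, and the 9.8% leaves out the three comparisons already planned.

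It also stands that section 6.2 does not give the control's source, size, selection, test methods or follow-up time. That is a question about the three comparisons that are planned. It does not show that a fourth or fifth is missing. It in fact weakens the case for adding them, because the documents do not say whether the control holds any acuity or defocus data. If it does not, the proposed contrasts cannot be run.

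**Conclusion.** The concern does not hold. It is true that 3 of 9 endpoints have a historical comparison, that 6 do not, and that the primary has none. But this contradicts nothing in the plan. A non-randomized pilot whose objective is to evaluate a lens pair may report its primary endpoint descriptively, and no conclusion about distance or near vision relative to bilateral Synergy is promised.

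The addition would be a confounded contrast with a half-width of roughly 0.37 to 0.48 SD, against 0.320 SD for the planned single-group mean. Those contrast figures rest on assumed control sizes of 100 down to 30. All logMAR values rest on assumed SDs, because section 6.1 says the SD is unknown. The conclusion itself depends on none of these assumptions. It follows from the objective, the endpoints and the pilot status as written. It would change only if the sponsor meant to claim better or worse vision than bilateral Synergy, and the documents contain no such claim.
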